Title: HCC Screening using DNA methylation Changes in ctDNA

ClinicalTrials.gov Identifier: NCT03483922

Date: January 11, 2022

Clinical study design

Study protocol was approved by IRB board of icddr,b (Dhaka, Bangladesh) study protocol PR-18025. 402 participants were recruited from the Dhaka area to the study included 49 healthy controls, 51 Chronic hepatitis B patients and 303 HCC patients from stages 0 to D (HCC O n=2, HCCA n=32, HCC B n=86, HCC C n=106, HCC D n=77 (See Table 2 for demographics). The age of the healthy control and the chronic Hepatitis B (CHB) groups were significantly younger 27 than the HCC group, however there was no significant effect of age on HCC prediction by DNA

methylation as determined by a logistic regression in either the HCC or control groups. However, in the CHB group age had a significant effect on HCC prediction by the DNA methylation test, consistent with the idea of a higher probability for older patients with chronic hepatitis to convert to HCC. There were no differences between the groups in the sex distribution. However, there was a somewhat significant lower alcohol use and higher fraction of smokers in the HCC groups (Table 2). HCC staging was diagnosed according to EASL–EORTC Clinical Practice Guidelines: Management of hepatocellular carcinoma. Hepatitis B diagnosis was confirmed using AASLD practice guideline for chronic Hepatitis B

(https://www.aasld.org/publications/practice-guidelines). All participants were properly informed about the study and have signed the informed consent form approved by the icddr,b IRB. Inclusions criteria were participants of either sex 18 to 70 years of age, confirmed diagnosis of HCC using EASL-EORTC guidelines and chronic hepatitis B using AASLD guidelines, nonmetastatic

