Bisulfate conversion was performed using EZ-96 DNA Methylation MagPrep (D5041, Zymo Research) followed by two rounds of polymerase chain reaction. For the first round we used primers that included an anchoring sequence and sequences targeting cg02012576 (CHFR), cg03768777 (VASH2), cg05739190 (CCNJ), cg24804544 (GRID2IP) and cg14126493 (F12) using Bio-Rad C1000 Touch Thermal Cycler (Bio-Rad Laboratories, CA, USA) (the primers are available upon request). 5 microliters of the first PCR reaction were subjected to a second round of PCR amplification using primers containing indexes for barcoding the samples (the primers are available upon request). PCR products were pooled, and the pooled library was then purified twice using AMPure XP Beads (Beckman Coulter Life Sciences, CA, USA) and quantified by RealTime PCR using NEBNext® Library Quant Kit for Illumina (New England Biolabs, MA, USA).

Sequencing was performed on the Illumina platform using MiSeq Reagent Nano Kit V2 (Illumina, CA, USA).

Statistical Analysis Plan

Significant difference from the control group was tested by Kruskal-Wallis non-parametric one-way ANOVA and was adjusted by Dunn's multiple comparisons test. The two HCC stage O samples were included for statistics in the HCC A group. ROC was computed using the ROC test in GraphPad.

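### The only accuracy analysis is an uncorrected ROC on the study cohort: no score, cut-off, source or comparator is stated, and nothing guards against optimism if the rule was tuned on these samples

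*Combined protocol and SAP*

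**What the plan says.** The Statistical Analysis Plan has three sentences. The first concerns group differences, not accuracy: "Significant difference from the control group was tested by Kruskal-Wallis non-parametric one-way ANOVA and was adjusted by Dunn's multiple comparisons test". The second merges the two stage 0 samples into stage A. The third is the whole of the accuracy analysis: "ROC was computed using the ROC test in GraphPad".

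The section on amplicon sequencing names five CpG targets, fixed by the primers, but gives no weights or combination rule. The Clinical study design section gives the cohort as "49 healthy controls, 51 Chronic hepatitis B patients and 303 HCC patients from stages 0 to D". It also reports that "in the CHB group age had a significant effect on HCC prediction by the DNA methylation test", whereas no age effect was found in the HCC or control groups, as judged by logistic regression. A prediction rule was therefore in use, but its formula, threshold and origin appear nowhere.

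Blinding is stated for the laboratory procedures only. No training/test split, cross-validation, bootstrap correction, external validation set or pre-locked rule is mentioned.

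**The concern.** Two things are missing, and they matter differently.

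The first is the comparator, which matters wherever the rule came from. The design section treats controls and chronic hepatitis B (CHB) patients as separate groups. The ROC could therefore set HCC against 49 healthy people, 51 CHB patients, or all 100. These are different questions, and for a study titled as HCC screening the choice decides what the specificity means.

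The second is the origin of the rule. If CpG weights or a cut-off were chosen on these samples, sensitivity and specificity at that cut-off will on average exceed what new patients would show. The plan has no step to correct this. As written, a reader cannot tell validation of a fixed test from derivation of a new one. A confidence interval does not solve this: it describes sampling error and leaves the bias in place.

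**Working it through.** **No design figure to reproduce.** The documents state no AUC, sensitivity, specificity, cut-off or sample-size target. The text can be checked for what it specifies; the size of any bias has to be simulated under assumptions.

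**Why a cut-off is inferred.** Logistic regression needs a two-valued outcome. Within the HCC, control or CHB group the diagnosis is constant, so the outcome is most naturally the test's positive/negative call, which requires a threshold. The outcome coding is not stated, so this is inference.

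**Inputs from the documents.** Healthy 49, CHB 51, HCC 303; pooled non-cases 49 + 51 = 100; stage 0/A 2 + 32 = 34. (The groups sum to 403 against a stated 402, which is immaterial here.)

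**Assumed inputs.** Score N(0, 1) in non-cases and N(d, 1) in cases, with AUC = Φ(d/√2), so d = √2·Φ⁻¹(AUC). True AUC 0.75, 0.85 and 0.92 give d = 0.95, 1.47 and 1.99.

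**Quantity computed.** For a cut-off c, true sensitivity is 1 − Φ(c − d) and true specificity is Φ(c). The excess is (observed sensitivity + observed specificity) − (true sensitivity + true specificity), both at the c that maximises the observed sum (Youden). For a c fixed beforehand the expected excess is 0.

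**Only the cut-off tuned here**, mean excess in percentage points across AUC 0.92 to 0.75:

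| Comparison | Sum | Sensitivity part | Specificity part |
|---|---|---|---|
| 303 HCC v 100 pooled | 3.3–4.6 | 0.8–1.2 | 2.4–3.4 |
| 303 HCC v 49 healthy | 4.6–6.5 | 0.6–1.0 | 4.0–5.5 |
| 34 stage 0/A v 51 CHB | 7.0–9.7 | 4.2–5.7 | 2.8–4.1 |

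The excess falls mainly on the smaller group, whose observed proportion is noisier. That is the non-cases in the first two rows and the cases in the third. The split shifts a little with where the cut-off is placed between adjacent observed values. In the first two rows, 17–20% and 14–18% of simulated data sets showed no excess.

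**Five weights also fitted here** (linear discriminant, independent and equally informative CpGs, then Youden): 4.4–6.9 points for 303 v 100, 6.5–10.1 for 303 v 49, and 11.8–17.7 for 34 v 51. The AUC itself is then overstated by 0.5–1.5 points (303 v 100) or 0.7–2.4 (303 v 49). If the score is fixed and only the cut-off is tuned, the AUC is unaffected.

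**Sensitivity to the assumptions.** With case SD three times the non-case SD, the cut-off-only excess is 2.3–2.9 (303 v 100) and 3.4–4.2 (303 v 49). With a cut-off set to reach 90% or 95% observed specificity, instead of Youden, it is 0.4–1.0 and 0.6–2.0.

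**Scale.** A hypothetical 90/100 specificity has an exact 95% interval of 82.4–95.1%, about 13 points wide.

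**Does validation remove it?** Stratified 10-fold cross-validation, with all selection repeated inside each fold, left −0.5 to +0.4 points of the sum for 303 v 100 and 303 v 49 (Monte Carlo SE 0.19–0.33). This was not simulated for 34 v 51.

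**The case against.** The strongest reply is that this is a reporting gap and not a demonstrated bias. The CpG sites were fixed in the primers before sequencing, the design section speaks of the test as something already defined, and a locked rule has no tuning bias at all. That stands. A reader might infer that the score or cut-off was optimised on these samples and that the resulting accuracy is inflated. The documents do not support that inference: they are silent on the rule's origin. Fixed sites do not settle the matter the other way either, because weights and a threshold can still be chosen afterwards, and the stated blinding does not reach the data analysis.

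A second reply is that the plan never says it will report sensitivity, specificity or a threshold, so the bias is sized for quantities it does not mention. This partly stands. The threshold is inferred from one clause, and for the AUC of a pre-fixed score the problem disappears. But a test described as predicting HCC needs a call rule, and the plan gives no source for one other than, possibly, this ROC.

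A third reply is that the magnitudes rest on assumed AUCs and distributions, and that for the pooled comparison the specificity part (2.4–3.4 points) lies well inside ordinary sampling error. Both statements are true. Calling the bias modest and mostly in specificity is not safe in general, however: for stage 0/A v CHB, the contrast closest to screening, it is about twice as large and falls mainly on sensitivity.

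**Conclusion.** The concern holds in conditional form. It is established that the ROC is the sole accuracy analysis, that score, cut-off, source and comparator are unstated, and that no internal validation is planned. It is not established that anything was tuned here.

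The size depends on which case applies. For a rule locked on outside data it is zero. For a Youden cut-off chosen here, the average overstatement of sensitivity plus specificity is about 3–5 points (303 v 100), 5–6 (303 v 49) or 7–10 (34 v 51), and more if weights were also fitted. These values rest on an equal-variance normal score with true AUC 0.75–0.92; they shrink if the case variance is larger or the cut-off targets a fixed specificity. This should be changed, but it does not by itself invalidate the study. The unnamed comparator needs resolving in every case.

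**What to change.** State whether the score and cut-off were locked on data outside this cohort. Run the ROC separately for HCC v healthy, HCC v CHB, and stage 0/A v CHB.

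- **If locked:** give the formula, the numerical cut-off and their source. Report sensitivity and specificity at that cut-off with exact 95% confidence intervals, overall and for stage 0/A and CHB. Cross-validation is then unnecessary.
- **If any weight or cut-off was chosen here:** replace the apparent figures with internally validated ones, using repeated stratified cross-validation or bootstrap optimism correction, with every selection step repeated inside each resample. Report sensitivity and specificity, and the AUC if weights were fitted, including for stage 0/A and CHB. Label the results derivation, not validation.

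Neither route needs new samples. The first costs a few lines of text and some exact intervals. The second costs a short script outside GraphPad, somewhat less favourable figures, wider uncertainty, and a weaker screening claim until a second cohort is tested.
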